These preliminary findings suggest that SCI disrupts multiple brain networks, along with significant alteration of resting state function of the paracingulate gyrus. Pain may modulate some of these properties, and notably disrupts local brain activity of the periaqueductal gray. The frequency band of ALFF alterations are similar to those of calcium channels and astrocytes, consistent with findings in post-traumatic neuralgia [Alshelh et al., 2016]. Further, the primary somatosensory region representing the lower torso displayed an increase in intrinsic connectivity in parallel with increased pain ratings. This may be consistent with phantom limb like pain, or an increased processing of denervated lower body sensations. Collectively, this work demonstrates feasibility and our expertise with the proposed imaging methodology. ALFF has high test-retest reliability and is thus suitable for longitudinal evaluations [Zuo et al., 2010]. Based on these findings, we hypothesize that brivaracetam treatment will normalize pain-related changes identified above, with ALFF of the periaqueductal gray being the primary outcome. Therefore, these findings provide the scientific rationale for the fMRI studies proposed in Aim 2.

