### *15.1 Data Analysis Plan:*

For aim 1, the main outcome variables of interest include various dimensions of pain, mood (PHQ-9), life satisfaction (SWLS), resting state brain connectivity, and community integration (CHART-SF) measured at baseline and again at 3-months of treatment. Of particular interest is whether there is a difference in pain reduction from baseline to end of study between the treatment and control groups; this will be analyzed in this pilot with linear regression including terms for group and time and the interaction of group by time. We note that many of these instruments have bounded scores and we will include analyses that recognize these (via, e.g., non- linearities or recognize the bounds such as Tobit regression) Further exploratory analyses will examine the relationships (correlations) between changes in pain and changes in mood, life satisfaction, resting state brain connectivity, and community integration using linear regression.

For aim 2, we will use the same analytic approach we have refined in our 2 active rsfMRI studies. MRI data will be analyzed using the SPM12 based Conn toolbox 3 (Version 17f, Matlab R2018b). Preprocessing steps include realignment and unwarping, slice-timing correction, ART based identification of outlier scans for scrubbing, segmentation and normalization to MNI space, and 8 mm smoothing. Denoising steps include scrubbing, aCompCor, ICA-based denoising, Global Regression, and 0.008 to 0.09 Hz band-pass filtering). Three main comparisons will be evaluated: The effect of drug treatment on rsfMRI measures, the effect of pain intensity on rsfMRI measures (each via linear regression as in Aim 1), and the differences in rsfMRI measures between active drug responders and non-responders; this last will also be analyzed via linear regression; note, however, that this will be limited to those in the active group and people in the placebo group will not be included. First, we will evaluate region-of-interest (ROI) based functional connectivity in a set of anatomically defined regions known to be impacted in SCI and neuropathic pain: the periaqueductal gray, the bilateral thalamus, the amygdala, the hippocampus, the insula, anterior cingulate, the precentral and the post-central gyrus. Second, we will evaluate, on a voxel-by-voxel basis, amplitude of low frequency fluctuations (ALFF) and intrinsic resting state functional connectivity.

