## MEDICAL PROTOCOL (HRP-590)

PROTOCOL TITLE: Brivaracetam to Reduce Neuropathic Pain in Chronic SCI: A Pilot Clinical Trial  
VERSION DATE: 03/18/2024

steps will be performed in the Statminer software suite: quality control of biological replicates, filtering of miRNAs expression having Ct values below cycles and the detection of expression in all biological replicates of calibrator and target. Statistically significant miRNAs will be selected based on stringent parameters such as Benjamin-Hochberg false discovery rate (FDR) and data will be conservatively selected with adjusted p-values and p-value lower than 0.01 and 0.05, respectively. Functional pathway analysis of altered miRNAs and their association with proteins related to reduction in neuropathic pain will be performed using Ingenuity Pathway Analysis (IPA) program (Ingenuity Systems Inc., Redwood City, CA). This software compiles known interactions for relevant miRNAs potential/ targets from published literature. This does not involve detection of genotypes, mutations, or chromosomal changes. For clinical correlation analysis, data comparing changes in miRNA expression will be described as means with standard error of the mean. In order to analyze the differences between group means we will use analysis of variance (ANOVA) after the assessing for distribution and variance. Multiple comparisons will be performed using Games-Howell test.

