### 15.2 Power Analysis:

Part of the goal of this pilot study is to obtain information that can be used for formal sample size estimation, including effect sizes and standard error estimates; therefore, analyses are included here that may not be included in a non-pilot follow-up (including the randomization analyses described below); further, some of the analyses here are exploratory to help in the design of a follow-up study. Also, (1) robust standard errors will be used in all cases to help guard against the effects of heteroskedasticity; (2) although there are a number of outcomes and, therefore, analyses, no adjustments for multiple comparisons will be made in this pilot study as the prime aim is not the level of statistical significance but rather the estimation of results needed for planning a follow-up. Of course, when disseminating our findings we will report the number of tests performed and the actual p-values so that readers can make their own adjustments if wanted.

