### 15.3 Statistical Analysis:

All statistical analyses will be conducted with Stata v. 16 (Copyright 1985-2019 StataCorp LLC, College Station, TX) or SAS v.9.4 (Copyright (c) 2002-2012 by SAS Institute Inc., Cary, NC, USA) assuming a 5% level of significance unless otherwise stated. Participant characteristics will be

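### The imaging outcome called primary, periaqueductal gray ALFF, has no defined contrast, and the plan conflicts with itself on whether Aim 2 results are corrected for multiplicity

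*Combined protocol and SAP*

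**What the plan says.** The Specific Aims in section 1.0 set Aim 2 as whether three months of brivaracetam lowers PAG activity. The end of section 2.2 fixes the measure: treatment is expected to normalize the pain-related imaging changes, "with ALFF of the periaqueductal gray being the primary outcome". Section 3.2 lists resting-state connectivity as the imaging secondary outcome and mentions neither ALFF nor the PAG.

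Section 15.1 opens Aim 2 by saying "we will use the same analytic approach we have refined in our 2 active rsfMRI studies". It lists three comparisons: drug treatment, pain intensity, and responders against non-responders within the active arm. All use linear regression. Two kinds of analysis follow. The first is region-of-interest (ROI) functional connectivity in eight named regions, one of them the PAG. The second is the voxel analysis: "Second, we will evaluate, on a voxel-by-voxel basis, amplitude of low frequency fluctuations (ALFF) and intrinsic resting state functional connectivity". No voxel, cluster or FDR threshold is given for either.

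On multiplicity, section 15.2 says "no adjustments for multiple comparisons will be made in this pilot study". Its reason is that "the prime aim is not the level of statistical significance but rather the estimation of results needed for planning a follow-up", and it promises that "we will report the number of tests performed and the actual p-values". Section 15.3 sets all analyses at one level, "assuming a 5% level of significance unless otherwise stated". For Aim 3, however, section 15.1 says "Statistically significant miRNAs will be selected based on stringent parameters such as Benjamin-Hochberg false discovery rate (FDR".

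**The concern.** Two things are left open that an analyst must decide, and both could be decided after the maps have been seen.

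The first is what the Aim 2 result is. A voxel map of ALFF offers many values in and around the PAG. Without a mask, a summary value and a contrast, the PAG effect could be a peak voxel, a cluster mean or an atlas mean. That matters for a pilot whose stated purpose (sections 1.1 and 15.2) is to supply effect sizes and standard errors for the next trial, because an estimate taken from a selected peak is biased upward.

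The second is what counts as a finding elsewhere in the brain. If the no-adjustment sentence governs the imaging, Aim 2 could report brain changes under treatment whether or not there are any. Reporting the number of tests and the p-values lets a reader adjust a handful of questionnaire scores. It does not let a reader adjust a smooth map of thousands of correlated voxels.

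**Working it through.** **1. The plan's own figure.** The plan gives no imaging threshold, familywise error rate or sample-size derivation to reproduce. The only stated figure is 5% per test (section 15.3; two-sided is assumed). For one test, 1 − (1 − 0.05)^1 = 5%.

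**2. Where PAG ALFF appears.**

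| Place | ALFF | PAG |
|---|---|---|
| Specific Aims, Aim 2 | not named | activity to decrease |
| Section 2.2 | primary imaging outcome, in the PAG | same |
| Section 3.2 | not named | not named |
| Section 15.1, ROI analysis | not used | one of the connectivity regions |
| Section 15.1, voxel analysis | whole map | not named |

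A model does exist: section 15.1 refers Aim 2 back to the Aim 1 regression with group, time and their interaction. With two time points, the interaction coefficient is the between-arm difference in mean change. What is missing is the dependent variable, a single PAG ALFF value per scan.

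**3. Which multiplicity rule applies.** Section 15.2 points to no correction. Three facts point the other way. Aim 2 is said to follow the earlier imaging approach. The description of that approach in section 2.2 also states no threshold, yet its imaging results are given as pFDR (PAG ALFF: 0.0009). And Aim 3 uses FDR in the same plan. The text does not settle the matter.

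**4. Voxel maps if uncorrected.** For m independent tests, the chance of at least one false positive is 1 − 0.95^m. The plan gives no voxel count, so effective tests are assumed.
- m = 100: 1 − 0.95^100 = 99.4%.
- m = 500: over 99.99%.

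A null simulation used 27,000 voxels on an assumed 3 mm grid, with 8 mm FWHM smoothing as in section 15.1 and t tests on independent smooth fields. It was run 100 times at 10 per arm and 100 times at an assumed low case of 6 per arm. Every run had at least one voxel below 0.05. The mean count was 1,364 at 10 per arm and 1,342 at 6 per arm, against an expected 0.05 × 27,000 = 1,350. An uncorrected 0.001 threshold also failed in every run.

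**5. ROI connectivity if uncorrected, treatment comparison only.** Section 15.1 says only that connectivity is ROI-based, so testing all pairs is an inference. Eight regions give 8 × 7 / 2 = 28 pairs. Splitting six paired regions into left and right gives 14 regions and 14 × 13 / 2 = 91 pairs. Expected false positives are 0.05 × 28 = 1.4 and 0.05 × 91 = 4.55. The chance of at least one is:

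| Correlation between pairs | 28 pairs | 91 pairs |
|---|---|---|
| Independent (formula) | 76.2% | 99.1% |
| 0.3 (simulated) | 65% | 94% |
| 0.5 (simulated) | 51% | 77% |
| 0.7 (simulated) | 34% | 52% |

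The simulated rows use 10 per arm and 4,000 runs. At 6 per arm they are 66%, 53% and 37% for 28 pairs, and 94%, 79% and 54% for 91. Ten per arm is the study-wide 20 in section 23.1 at 1:1. Section 5.1 instead has 20 at each of two sites, and MRI is optional, so the imaging sample is unknown, but the rates barely change between 10 and 6 per arm.

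**6. After the change proposed below.** One prespecified PAG ALFF test at 0.05 has a 5% false-positive rate. Each exploratory family held at FDR or familywise error 0.05 has at most a 5% chance of any false positive under the global null. For scale, Bonferroni levels for ROI pairs would be 0.05/28 = 0.0018 or 0.05/91 = 0.00055.

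**The case against.** The best defense is that section 15.2 concerns multiplicity across a number of outcomes and says nothing about thresholds inside a voxel map. The same plan sets an FDR rule for miRNAs, so the general sentence was probably not meant to bar correction within a high-dimensional family. The imaging text in 15.1 closely follows the preliminary description in 2.2, which was also silent on thresholds and still led to pFDR results. This is a fair reading. A reader might infer that the plan forbids correction of the imaging results, and the documents do not support that. They support a conflict that remains unresolved.

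It is also fair that the no-adjustment choice is disclosed and justified by estimation, and that the primary endpoints in section 3.1 are safety and the Brief Pain Inventory. Stray voxels elsewhere would not confirm a hypothesis about the PAG. But an estimation aim makes the missing PAG summary value more important, since that is the quantity to be estimated.

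Two further inferences should be resisted. One is that false-positive treatment effects are near certain throughout Aim 2. Only one of the three comparisons is a treatment effect, and near certainty holds for the voxel maps, not for ROI connectivity alone. The other is that 8 mm smoothing removes most of the PAG signal. The documents give no PAG size or voxel grid, and the preliminary PAG result came from the same smoothing.

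**Conclusion.** The point holds in this form. The outcome called primary for imaging has a regression model but no defined measure or named contrast, and the plan gives conflicting signals on correction with no imaging threshold to settle them. The first part rests on the text alone and stands however multiplicity is resolved.

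The error rates are conditional on reading section 15.2 literally at 5% under a global null. For voxel maps, at least one false-positive voxel is then practically certain for any plausible voxel count. For ROI connectivity in the treatment comparison the range is about 34% to 99%. Voxel count, left/right split, correlations and imaging sample size are assumptions, and the simulations used t tests instead of the planned regression with robust standard errors.

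This should be fixed, but it does not threaten the trial's primary conclusions: imaging is secondary and optional in a pilot aimed at planning.

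**What to change.** - **Section 15.1, Aim 2:** name one main test, the between-arm difference in change of mean ALFF within one anatomical PAG mask, estimated by the group-by-time term already planned. Fix the mask before unblinding and report the estimate with its confidence interval. Extraction from unsmoothed data is at most a sensitivity analysis.
- **Section 15.1, remaining imaging:** report ROI connectivity with FDR and the voxel maps with a stated voxel- or cluster-level correction. State how many connections are tested, and label all of it exploratory.
- **Section 15.2:** limit the no-adjustment sentence to the clinical scales, so that it no longer conflicts with the FDR rule for miRNAs or with the imaging approach carried over.
- **Section 3.2:** list PAG ALFF among the imaging outcomes.

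The cost is a few sentences and one ROI extraction, with no new visits or participants. The price is fewer nominally significant imaging results. The revision history marks enrollment as complete, so the change should be dated and made before any unblinded imaging analysis. The documents do not say whether that has begun.

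The change does not give the PAG test high power. At 10 per arm, by the normal approximation, 80% power needs a difference of (1.96 + 0.84) × √(2/10) = 1.25 SD, which is another reason to present the result as an estimate.

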### 1.0 Objectives

#### 1.1 Purpose:

SCI is associated with severe neuropathic pain that is often refractory to all pharmacological intervention. Our preliminary data suggest brivaracetam is a mechanism-based pharmacological intervention for neuropathic pain in SCI. In this project we will conduct a randomized, placebo-controlled pilot clinical trial to assess feasibility of a 3-month treatment course with brivaracetam. We will assess changes in pain intensity and periaqueductal gray hyperactivity. We will assess baseline periaqueductal gray hyperactivity and microRNA levels as potential biomarkers of response to treatment. We will use these preliminary findings to design larger clinical trials to establish efficacy of brivaracetam to treat neuropathic pain in SCI. The pilot data are necessary to adequately power the larger clinical trial based on SCI-specific data for each outcome of interest. Here we will be able to present the scientific evidence base supporting the rationale for this project.

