#### Specific Aims:

1. Specific Aim 1: Determine whether a 3-month course of daily brivaracetam is safe and effective at reducing severe below-level neuropathic pain after SCI.
2. Specific Aim 2: Determine whether a 3-month course of daily brivaracetam decreases periaqueductal gray activity in SCI.
3. Specific Aim 3: Determine whether baseline microRNA levels are associated with response to brivaracetam treatment.

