### 2.2 Preliminary Data:

SCI is associated with a high prevalence of severe below-level neuropathic pain that is often refractory to therapeutic interventions. Our preliminary work demonstrates overexpression of the synaptic vesicle protein 2A (SV2A) in electrically hyperactive substantia gelatinosa surgical samples in patients with neuropathic pain. The FDA-approved antiepileptic drug brivaracetam targets and binds to the SV2A protein with greater binding affinity than other drugs targeting SV2A. We have used brivaracetam off-label for compassionate reasons in severe, refractory neuropathic pain with sustained pain relief. We have identified multiple brain networks altered in SCI and modulated by neuropathic pain. Neuropathic pain also increases local brain activity of the periaqueductal gray. miR-485 regulates presynaptic expression of SV2A as well as dendritic spine density and synapse morphology and function. Therefore, circulating miR-485 may be a mechanism-based predictive biomarker of response to therapies targeting the SV2A protein, including brivaracetam. These findings, paired with our preliminary data, suggest that reduced levels of miR-485 may contribute to the pathophysiology of SCI-induced neuropathic pain by disrupting normal levels of SV2A and neural network activity in nociceptive neurons. Collectively, these findings provide the scientific rationale for the following hypotheses to be tested in this pilot clinical trial: compared to placebo, treatment with brivaracetam reduces severe below-level SCI neuropathic pain with corresponding reduction in periaqueductal gray brain activity by rsfMRI (Aim 1). We also hypothesize that either periaqueductal gray brain activity or circulating miRNA-485 may be candidate predictive biomarkers of response to brivaracetam therapy. Collectively, the results of this pilot clinical trial will be used to design larger clinical trials to confirm these hypotheses.

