## MEDICAL PROTOCOL (HRP-590)

PROTOCOL TITLE: Brivaracetam to Reduce Neuropathic Pain in Chronic SCI: A Pilot Clinical Trial  
VERSION DATE: 03/18/2024

That is, we hypothesize that individuals with lower circulating miR485 levels may be less likely to respond to brivaracetam treatment for neuropathic pain than those with higher circulating miR485.

miRNAs are promising molecules with potential use as prognostic and diagnostic biomarkers of neuropathic pain and also as predictive biomarkers to monitor the effect of treatments for neuropathic pain in humans. However, the lack of properly conducted clinical studies prevents the bench-to-bedside translation of this knowledge to the clinical setting. This project aims to address these gaps by studying the role of miRNA in SCI neuropathic in humans as well as miRNA signatures as predictive biomarkers of response to brivaracetam therapy in SCI. This evidence provides the scientific rationale for the studies proposed in Aim 3.

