For aim 3, we will analyze miRNA expression profiles for raw cycle threshold (Ct) values using real-time Statminer software (Integromics, Inc) to identify significantly altered miRNAs. For relative quantification of miRNAs between placebo and brivaracetam-treated samples, the following

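### Section 15.1 never relates baseline microRNA to pain response, so Aim 3, followed as written, gets no estimate

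*Combined protocol and SAP*

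**What the plan says.** The question is stated four times. The Specific Aims give Aim 3 as "Determine whether baseline microRNA levels are associated with response to brivaracetam treatment". Section 1.1 (Purpose) adds "We will assess baseline periaqueductal gray hyperactivity and microRNA levels as potential biomarkers of response to treatment". Section 2.2 narrows this to one marker, proposing that "either periaqueductal gray brain activity or circulating miRNA-485 may be candidate predictive biomarkers of response to brivaracetam therapy", and Section 2.3 gives the direction: "individuals with lower circulating miR485 levels may be less likely to respond to brivaracetam treatment". Section 3.1 defines response as a BPI fall of at least 1 point.

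The Aim 3 analysis in Section 15.1 begins "For relative quantification of miRNAs between placebo and brivaracetam-treated samples, the following" and lists quality control, filtering, selection of altered miRNAs by false discovery rate, and a pathway analysis based on published literature. It then says: "For clinical correlation analysis, data comparing changes in miRNA expression will be described as means with standard error of the mean". Group means are to be compared by ANOVA, with Games-Howell for multiple comparisons. The groups are not named.

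Elsewhere in Section 15.1, the exploratory Aim 1 regressions relate "changes in pain and changes in mood, life satisfaction, resting state brain connectivity, and community integration using linear regression". Aim 2 includes a comparison of responders with non-responders in the active arm, for rsfMRI measures.

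**The concern.** The aim and its analysis do not meet. The aim needs a baseline marker on one side and pain response on the other. The first planned contrast has arm on one side and miRNA on the other, which asks whether the drug alters miRNA. The second names a quantity (changes) but no clinical variable.

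Section 15.2 says the pilot exists mainly to supply estimates for planning a later trial. For the biomarker question, the plan as written would supply none. An analyst would have to choose the model after the data are in, or might present the arm contrast as if it answered Aim 3.

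**Working it through.** The plan gives no sample size, effect size or SD for Aim 3, so there is no figure to reproduce. The main check is of the text.

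**1. Aim against plan**

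| Element | Aims and background | Section 15.1, Aim 3 |
|---|---|---|
| Marker | miRNA; miR-485 named | miRNAs in general; miR-485 not named |
| Time point | Baseline | Not stated; changes described |
| Outcome | BPI response | Does not appear |
| Groups | Implied by response | Placebo and brivaracetam; ANOVA groups unnamed |

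The Aim 1 exploratory regressions omit miRNA, and the Aim 2 responder comparison covers imaging only. The pathway step mentions pain-related proteins, but it draws on literature and not on participants' outcomes. Section 15 runs continuously in the text supplied, so the gap does not come from a removed page.

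**2. If changes means change over time**

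Let *r* be the correlation of pain improvement with baseline level and ρ the test-retest correlation of the marker, with equal variance at both visits and nothing else acting. With unit variances, cov(improvement, change) = rρ − r = −r(1 − ρ), and var(change) = 2(1 − ρ). Hence

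corr(improvement, change) = −r√((1 − ρ)/2).

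For an assumed r = 0.5:

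- ρ = 0.5: −0.5 × √0.25 = −0.25
- ρ = 0.8: −0.5 × √0.10 = −0.16
- ρ = 0.9: −0.5 × √0.05 = −0.11

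On this reading, change carries a weaker association of opposite sign and is a poor stand-in for baseline level.

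**3. The arm contrast**

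Response is not a term in it, so its result does not depend on *r*. In simulation with no drug effect on miRNA, it rejects in 5.3%, 5.1% and 4.8% of trials with 6, 10 and 20 per arm. If the drug shifts the change by 0.5 SD, it rejects in 12%, 19% and 34%; by 1 SD, in 35%, 56% and 87%. It responds to a drug effect on miRNA, which is a different question.

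**4. What the missing analysis could deliver**

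Numbers per arm: Section 5.1 gives 20 per site at two sites, so 40 in all and about 20 per arm at 1:1. Section 23.1 gives 20 study-wide, about 10 per arm. Research blood is optional and virtual participants give none (Section 5.2). Uptake is not stated, so 6 per arm is an assumption.

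Model: outcome (SD 1) on baseline BPI, arm, marker and arm-by-marker; *r* = 0.5 in active and 0 in placebo; baseline BPI unrelated to outcome; HC3 variance, *t* reference with N − 5 degrees of freedom; 20,000 simulated trials per case.

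| Usable per arm | Median 95% half-width, active-arm slope | Median 95% half-width, interaction | Interaction power |
|---|---|---|---|
| 6 | 1.48 | 2.52 | 3.7% |
| 10 | 0.77 | 1.26 | 10.5% |
| 20 | 0.44 | 0.70 | 28.1% |

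If baseline BPI correlates 0.5 with outcome, the half-widths fall to 1.22, 0.63 and 0.36 (slope) and 2.14, 1.06 and 0.59 (interaction).

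With *r* = 0.5 in both arms, so that no interaction exists, the interaction test at a nominal 5% rejects in about 2%, 3% and 4% of trials with HC3, 11%, 9% and 7% with HC1, and 5% with ordinary standard errors. Section 15.2 requires robust standard errors without naming a form, and at these sizes the form matters.

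**The case against.** **The text can be read more kindly.** The step is labelled as a clinical correlation. Games-Howell adds little with only two arms, so other groups, perhaps responders and non-responders, may be meant. In an account of relative quantification, changes can mean differences in expression between groups and not change over time. This stands in part: the time point, groups and clinical variable are undefined, and the text does not settle on change over time. A reader might infer that the planned analysis must reverse the sign of a true baseline association. The documents do not support that, because step 2 applies on one reading only. Still, no reading puts both baseline level and BPI response on the page.

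**The arm contrast might look uninformative by construction.** A reader might infer from a 5% rejection rate that it finds nothing whatever happens. That rate assumes the drug leaves miRNA unchanged; step 3 shows it rising otherwise. The supportable point is narrower: response is absent from the contrast.

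**An interaction model asks more than Aim 3 does.** For responder questions the protocol's own Aim 2 habit is to use the active arm alone, and a simple active-arm correlation of 0.5 would be detected in about 17%, 32% and 64% of trials with 6, 10 and 20 participants. This is fair. The active-arm slope should therefore be reported as the answer to the association question. The interaction is still needed before the marker is called predictive, the word used in Section 2.2, because the active arm alone cannot separate predictive from prognostic.

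**This is an exploratory pilot.** True, and it limits the severity. It does not supply the missing estimate.

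**Conclusion.** The gap is real and should be fixed: Aim 3 as analysed in Section 15.1 yields no estimate of the association between baseline miRNA and pain response. This rests on the text alone and needs no assumption. The primary endpoints in Section 3.1 are unaffected.

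The numerical illustrations rest on assumed values of *r*, ρ and blood uptake, and on unbounded normal outcomes. BPI scores are bounded and entry requires daily average pain of 9 or 10, so the precision figures are a guide only. They show that even the right analysis will be imprecise: with 10 per arm, the typical interval around an active-arm slope of 0.5 includes zero.

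A reader might also infer that the repair uses results already in hand. The documents do not show this. The revision history records only that enrolment was complete at version 8.0, Section 6.1 stores blood for batch processing, and Section 16.8 speaks of sending samples for assay in the future tense.

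**What to change.** Add to Section 15.1, before Aim 3 data are analysed by arm (if that has already happened, label the model post hoc):

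> In all participants with a baseline miR-485 result, the 3-month BPI pain intensity score (the same named item as for Aim 1) will be regressed on baseline BPI, arm, baseline miR-485 and arm-by-miR-485. The slope in the brivaracetam arm (association with response) and the interaction (predictive versus prognostic) will be reported with 95% confidence intervals as exploratory estimates. The variance estimator will be HC3 with a t reference; ordinary standard errors will be a sensitivity analysis. Baseline miR-485 will also be summarised by the 1-point response within each arm.

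Because the outcome is the 3-month score, the Section 2.3 hypothesis predicts a negative slope in the brivaracetam arm. HC3 is one suitable small-sample choice, not the only one; what matters is naming the estimator in advance.

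Four further edits:

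- Name the BPI item. Section 5.2 lists worst, least, average and present pain.
- Apply the false discovery rate screen to the association of baseline level with response across the wider panel too, since Aim 3 is not limited to miR-485. Keep the arm contrast as a separate question about drug effect on miRNA.
- State that this screen is an exception to the rule in Section 15.2 against adjusting for multiplicity.
- Define the groups and time point of the ANOVA.

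Cost: plan wording and a modest analysis, with no participants or blood draws beyond those already planned (Section 6.1). Assays may still have to be run. The number with usable blood will probably fall below the number enrolled, so results should be presented as planning estimates with their intervals.
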